8.4 Treatment of Overdose

For this study, any dose higher than the calculated dose for that particular administration within a 12-hour time period is considered an overdose.

The Sponsor does not recommend specific treatment for an overdose, but the Investigator should use his or her clinical judgment when treating an overdose of the study intervention considering the presenting symptoms and standard evaluation results.

For monitoring purposes, any case of overdose, even if not associated with an AE or a SAE, any overdose is recorded in the eCRF and reported to drug safety in an expedited manner. Overdoses are reported on a SAE Report Form, following the procedure in [Appendix 5](#), section on reporting SAEs.

8.5 Pharmacokinetics

Sampling time schedules for determination of M3258 can be found in [Table 5](#) for Part A and for M3258 and dexamethasone in [Table 6](#) for Part B. Whole blood samples of approximately 40 mL in Cycle 1 of Part A will be collected for measurement of plasma concentrations of M3258; whole blood sample of approximately 30 mL in Cycle 1 and 30 mL on Cycle 2 of Part B will be collected for measurement of plasma concentrations of M3258 and dexamethasone. The actual date and time (24-hour clock time) of each sample will be recorded to calculate actual time elapsed since the prior dose administration. Details on processes for collection and shipment of these samples are in Laboratory Manual.

The quantification of M3258 and dexamethasone in plasma will be performed using a validated assay method. Concentrations will be used to evaluate the PK of study intervention.

Remaining samples collected for analyses of plasma concentration may also be used to evaluate metabolites safety or efficacy aspects related to concerns arising during or after the study.

The definitions for PK parameters are listed in [Appendix 8](#).

Details on processes for collection and shipment of these samples are in the Laboratory Manual. Retention time and possible analyses of samples after the end of study are specified in the respective ICF.

8.6 Pharmacodynamics

Pharmacodynamic markers are described in Section 8.8, and details on processes for collection and shipment of these samples are in the Laboratory Manual.

CCI [REDACTED]

[REDACTED]

[REDACTED]

[REDACTED]

8.8 Biomarkers

- Collection of participant samples for biomarker research is also part of this study and is governed by the appropriate ICF.
- The following participant samples for biomarker research are required and will be collected from all participants in this study, as specified in the SoAs (Table 1 and Table 2 for Part A; Table 3 and Table 4 for Part B):
 - Blood samples for analysis of L-citrulline, β 5c activity in whole blood and LMP7 activity in PBMCS.
 - Bone marrow sample for determining cytogenetic risk factors and minimal residual disease (MRD).
 - Baseline bone marrow samples to identify cytogenetic risk factors in order to evaluate associations with drug response.
 - Baseline bone marrow samples to determine MM clonality before treatment, which is needed as a reference when evaluating MRD (i.e. disease burden) using next generation sequencing (NGS) for participants that experience a CR or sCR.
 - On-study bone marrow aspirate to determine MRD in participants experiencing CR or sCR using NGS and/or next generation flow cytometry. Of note, only participants that experience a CR or sCR will have their baseline sample analyzed using NGS, whereas next generation flow cytometry does not require a baseline sample.

A portion of the bone marrow sample to confirm CR (including sCR), as described in Section 8.1, will be sent to a laboratory for MRD assessment by next generation flow cytometry and/or next generation sequencing.

In addition, participant samples may be used for additional research, as specified in the ICF.

Details on processes for collection and shipment of these samples are in Laboratory Manual. The Sponsor will store the samples in a secure storage space with adequate measures to protect confidentiality. Retention time and possible analyses of samples after the end of study are specified in the respective ICF.

8.9 Health Economics

Not applicable.

8.10 Immunogenicity Assessments

Not applicable.

9 Statistical Considerations

9.1 Statistical Hypotheses

This is an exploratory study. No formal statistical hypothesis will be tested.

9.2 Sample Size Determination

Dose Escalation Part A

The planned cohort size is 3 participants at a given dose. Parallel screening and enrollment of participants will allow eligible participants to enroll, the cohort size may therefore increase to a maximum of 4 participants. Any additional participants enrolled in the study at a given dose, will complete all study procedures and assessments as per protocol and are considered in the Bayesian model if they fulfill the criteria for inclusion in the DLT set.

The total sample size will depend on the number of cohorts and regimens to be evaluated. It is anticipated that 15 to 21 participants (4 projected dose levels with 3 to 9 participants each) may be needed. If change(s) in regimen would occur, the sample size may increase.

The following scenario is anticipated:

2 dose levels with 3 participants each and 2 dose levels with 6 participants each, resulting in 18 participants.

Considering for example one change in regimen after the first dose level, the sample size may increase by 3 if in the new regimen, the above scenario holds.

Dose Expansion Part B

Part B begins with a safety run-in of 6 participants. Dose adjustments during Part B may occur.

Part B will include 30 participants treated at the same dose who are evaluable for response in a two-stage design. This sample size will give a posterior probability of 85% that the ORR \geq 20% if 8/30 responses are seen at the final analysis.

An interim analysis will occur after enrollment of 15 participants treated at the same dose are evaluable for response. The cut-off for the interim analysis was chosen to balance sufficient information for decision with the potential of sparing participants an inefficient treatment. The boundary and operational characteristics are described in Section 9.4.1.

If in the course of the expansion and/or at the interim analysis, the M3258 dose is modified, then only participants treated at the same dose will be considered in the two-stage design. Therefore, the number of participants in the expansion cohort might increase by approximately 3 to 21 participants to reach the required number of 30 participants treated on the same dose who are evaluable for response according to IMWG.

Additionally, in Part B (as well as in Part A) the SMC may recommend to end the enrollment in the expansion cohort due to safety concerns.

9.3 Populations for Analyses

The analysis populations are specified below. The final decision to exclude participants from any analysis population will be made during a data review meeting prior to database lock.

Analysis Set	Description
Screening (SCR)	All participants, who provided informed consent, regardless of the participant's randomization and study intervention status in the study.
Safety (SAF)	All participants, who were administered any dose of any study intervention. Analyses will consider participants as treated.
DLT	The Dose Escalation Set will include all participants who received at least one dose of study intervention and meet at least one of the following criteria: 
 Experienced at least one DLT during the DLT period, regardless of the administered number of doses of study intervention/completion of the DLT period Received at least 80% of the planned cumulative dose and 80% of planned administrations of each treatment during the DLT period and completed the DLT period.
PK	All participants, who receive at least one dose of study intervention, have no clinically important protocol deviations or important events affecting PK, and provide at least one measurable postdose concentration. Participants will be analyzed per the actual study intervention they received.
Pd	All participants, who receive at least one dose of study intervention, have no clinically important protocol deviations or important events affecting Pd, and provide at least one measurable Pd endpoint postdose.

DLT = Dose-limiting toxicity; Pd = Pharmacodynamics; PK = Pharmacokinetics.

9.4 Statistical Analyses

There is no formal significance level for this study, and all analyses are considered descriptive.

9.4.1 Efficacy Analyses

Endpoint	Statistical Analysis Methods
Primary	No primary efficacy endpoint is specified

Secondary	Will be specified in the Integrated Analysis Plan finalized before database lock. In general, continuous variables will be summarized using number of participants (n); mean, standard deviation; median, 25 th Percentile to 75 th Percentile (Q1-Q3), minimum, and maximum. If there are less than 5 observations available, only mean and the observed data will be given. Categorical variables will be summarized using frequency counts and percentages. The calculation of proportions will be based on the number of participants in the analysis set of interest, unless otherwise specified in the study Integrated Analysis Plan. Kaplan-Meier estimates (product-limit estimates) will be presented for the analysis of PFS and OS together with a summary of associated statistics (median survival time, 6-, 12-month survival rate estimates and estimates for every 6 months thereafter if applicable) including the corresponding 2-sided 95% CIs.
Tertiary/Exploratory	Will be specified in the Integrated Analysis Plan finalized before database lock.

CI = Confidence Interval; PFS = Progression-Free Survival; OS = Overall Survival.

In Part B, a two-stage design with an interim analysis after 15 participants treated on the same dose and evaluable for response is foreseen. If less than 3 responses are seen out of 15 participants evaluable for response, the expansion cohort is stopped for futility or dose is increased. This gives a probability of falsely stopping the study if the drug were effective (assuming an ORR of 35%) of 6%, while already correctly stopping the study if the drug is not sufficiently effective (assuming an ORR of 15%) of 60%. Else the study continues, until 30 participants are evaluable for response.

At this interim analysis there is the possibility to:

- If ≥ 3 responders are seen (in participants treated on the same dose) and there are no safety concerns, continue the study on the same dose until 15 additional participants are treated at the same dose who are evaluable for response according to IMWG, or
- If < 3 responders are seen, either:
 - Stop the study for futility, or
 - Increase the dose (within the limits specified in Section 4.1 and only to doses with an estimated 75% percentile of the DLT rate below 30% from the Bayesian model in combination will be considered). Enroll participants at the new dose until 15 participants treated at the new dose are evaluable for response according to IMWG. Subsequently a new interim analysis is performed. The following options at that second interim analysis are possible (the same futility rule as for the first interim applies after 15 participants treated on the same dose who are evaluable for response):
 - If ≥ 3 responders (in participants treated on the same dose) are seen and there are no safety concerns: Continue at the same dose until additional 15 participants are evaluable for response (to reach overall 30 participants on the changed dose evaluable for response), or
 - If < 3 responders are seen, stop the study for futility.

If any other option is deemed necessary, a protocol amendment will be submitted.

No more than 2 such interim analyses will be performed, unless a protocol amendment is submitted.

Treated on the same dose includes all participants who were planned to receive the same dose.

9.4.2 Safety Analyses

Analyses to decide on dose escalation will be based on safety, PK, and Pd data.

To support the decision on dose escalation, the SMC will receive results of a Bayesian dose-toxicity model, including the recommendation of next dose level from the model.

The Bayesian dose-toxicity analysis will be performed on the dose escalation set.

More details of this Bayesian two-parameter logistic regression model ([Neuenschwander et al. 2008](#)) are further specified in [Appendix 10](#).

For each SMC meeting, the model will be updated with the number of DLTs and evaluable participants per dose level. Based on the observed data the model will suggest the next dose level. The following dose levels are foreseen: 10 mg, 20 mg, 35 mg, and 50 mg. However, the SMC may decide to have different or additional dose levels or skip dose levels, except escalation may not proceed to any dose higher than 50 mg. In case escalation should proceed to doses higher than 50 mg, an amendment will be submitted.

The dose suggested by the model for the next cohort will be the dose with minimal Bayesian Risk (among all considered doses).

The target DLT toxicity for the MTD is 25%.

The SMC may choose a different dose than suggested by the Bayesian escalation approach (not higher than 50 mg). Also, the SMC may decide to change the dosing regimen as specified in Section [4.1](#). In such a case the dose toxicity model will be extended, or a separate model will be set up.

Usually decisions on dose escalation are taken once all participants of the most recent cohort have completed the DLT period or discontinued. In exceptional cases, however, the SMC may recommend on the next cohort earlier, i.e., before the last participant of a cohort has finished the DLT period (considering the available data from the current and previous cohorts as well as model recommendation). Per definition of the Dose Escalation set, participants who have not completed the DLT period are not included for update of the model, unless they experienced a DLT. However, data of such participants will be included at next SMC (if criteria for the Dose Escalation set are then fulfilled).

Before first dosing, the assumed relationship between dose level and toxicity is specified through the prior distribution. The prior distribution chosen for this study correspond to the following mean/median estimates of DLT probability:

Probability for DLT	10 mg	20 mg	35 mg	50 mg
Prior mean	15%	19%	24%	28%
Prior median	8%	13%	18%	22%

DLT = Dose-limiting toxicity.

Details of the model, including the prior distribution can be found in [Appendix 10](#).

Decisions of the SMC in the expansion cohort will also be aided by a Bayesian two-parameter logistic regression model with the same specifications as for the dose escalation, except the prior. The prior will be based on the data seen in the monotherapy dose escalation and specified in the SMC charter before the first SMC for the expansion cohort occurs. The model will be updated at times of SMCs in the expansion cohort. Additional stopping rules in Part B apply (see Section [7.1](#)).

Other specifications are as for dose escalation and can be found in [Appendix 10](#).

Details on analyses for SMCs will be described in the SMC Integrated Analysis Plan.

All other safety analyses will be performed on the Safety Analysis population.

Endpoint	Statistical Analysis Methods
Primary (DLTs)	After end of dose escalation and main analysis, the number and proportion of participants experiencing DLTs will be reported by dose level, based on observations during the first study intervention cycle. Posterior probabilities (2.5%, 25%, 50%, 75%, and 97.5% quantiles) for DLT probabilities at selected doses will be estimated from the Bayesian logistic regression model. A sensitivity analysis will be performed using frequentist modeling (without prior).
Secondary	In general, continuous variables will be summarized using number of participants (n); mean, standard deviation; median, 25 th Percentile to 75 th Percentile (Q1-Q3), minimum, and maximum. If there are less than 5 observations available only mean and the observed data will be given. Categorical variables will be summarized using frequency counts and percentages. The calculation of proportions will be based on the number of participants in the analysis set of interest, unless otherwise specified in the study Integrated Analysis Plan. Details will be specified in the Integrated Analysis Plan finalized before database lock.
Tertiary/Exploratory	Details will be specified in the Integrated Analysis Plan finalized before database lock.

DLT = Dose-limiting toxicity.

QT/QTc Analysis

The ECG parameter will be summarized by descriptive statistics per time point; changes from Baseline will be calculated.

Time-matched, replicate ECGs and PK samples collected in the dose escalation phase will be used to analyze for cQTc responses using slope analysis of exposure/response. This analysis may be reported separately.

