- Twice-per-week dosing on Days 1, 4, 8, and 11, no dosing on Days 12 to 21, in 21-day cycles

If a switch in dose and/or regimen is recommended, the first tested dose level in the new regimen must not exceed the highest tested daily dose or the weekly cumulative dose must be equal to or lower than the highest weekly cumulative dose of regimen(s) tested so far.

The selected M3258 dose and regimen (RDE) will be combined with dexamethasone for the expansion cohort (Part B).

Dexamethasone will be given at a cumulative dose of 40 mg/week:

- 20 mg/day at Days 1, 4, 8, 11, 15, 18, 22 and 25 in a 28-day cycle

OR

- 20 mg/day at Days 1, 4, 8, 11, 15, and 18 in a 21-day cycle (regimen with drug holiday)

Dose Escalation Part A

Participants with MM whose disease has progressed following > 3 lines of therapy and for whom no effective standard therapy exists (see definition in Section 5) will be enrolled in the dose-escalation part of this study. The first dose escalation cohort will receive M3258 at the starting dose of 10 mg QD as a single agent. For further dose cohorts, a SMC will meet and review all available data to provide recommendations on the next dose level. The MTD is defined by the SMC with a target DLT rate of 25%. The following prespecified doses of 10

mg, 20 mg (100% increase), 35 mg (43% increase) and 50 mg (30% increase) are planned unless MTD is reached. The SMC, following review of preliminary safety, tolerability, PK and Pd information, will recommend the dose and/or the switch to an alternative regimen pre-specified in this protocol for the next cohort as applicable.

This may include proposing smaller dose increases compared to the prespecified doses and deescalation of the dose potentially down to 1mg.

The SMC may also recommend expanding a given cohort at the same dose level.

If additional dose levels above 50 mg are justified following review of preliminary safety, tolerability, PK, and Pd information from the initial cohorts, a protocol amendment will be submitted.

Depending on the observed toxicity profile, the SMC may decide on different doses as prespecified and/or change to regimens specified in this protocol. However, escalation may not proceed to any dose higher than 50 mg. In case escalation is recommended to proceed to doses higher than 50 mg, an amendment will be submitted. At each dose level, the first participant enrolled will be observed for DLTs for at least 48 hours before further participants are enrolled.

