If a clinically significant finding in ECG recording is identified (including, but not limited to changes from Baseline in QT interval corrected using Fridericia's formula [QTcF]) after enrollment, the Investigator or qualified designee will determine if the participant can continue in the study and if any change in participant management is needed. This review of the ECG printed at the time of collection must be documented. Any new clinically relevant finding should be reported as an AE.

The SoA (Table 1 and Table 2 for Part A; Table 3 and Table 4 for Part B) specifies the data to collect at study intervention discontinuation and Follow-Up, and any additional evaluations that need to be completed.

If a participant's study intervention must be discontinued, this will not result in automatic withdrawal of the participant from the study and the participant should be assessed at the End-of-Treatment visit and Safety Follow-Up visit.

A participant's study intervention should be discontinued if:

- The Investigator believes that for safety reasons (eg, AE) it is in the best interest of the participant to discontinue study intervention.
 - The participant becomes pregnant.
 - The participant (or the participant's legally authorized representative) withdraws consent for administration of study intervention.
 - The participant's dose is held for more than 5 days per cycle, or if ≥ 6 consecutive planned doses of M3258 are missed for reasons other than toxicity unless, upon consultation with the Sponsor and the review of safety and efficacy, continuation is agreed upon.
 - The participant experiences disease progression.

Safety Stopping Rules for Study Intervention in Part B:

Unacceptable toxicity in the expansion cohort is defined as AEs that meet the DLT criteria regardless of when they occur during treatment (as defined in Section 6.6). The following stopping rules for unacceptable toxicity apply:

- ≥ 5 participants with observed DLT criteria out of 12 evaluable participants treated on the same dose.
- ≥ 7 participants with observed DLT criteria out of 18 evaluable participants treated on the same dose.
- ≥ 9 participants with observed DLT criteria out of 24 evaluable participants treated on the same dose.
- The chance is $>80\%$ that the true DLT rate is $\geq 30\%$ (based on Bayes model).

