Appendix 10 Description of the Bayesian Dose Escalation Model

The Bayesian model is based on the number of DLTs and evaluable participants per dose level. The SMC will receive results of a Bayesian two-parameter logistic regression model updated with the observed DLT data (Neuenschwander et al. 2008), including a recommendation for the next dose. For a dose level d_j , the relationship between dose and probability of toxicity P (DLT) is defined by:

$$P(DLT|d_j, \alpha, \beta) = \frac{\exp\left(\alpha + \exp(\beta) * \log\left(\frac{d_j}{d_{ref}}\right)\right)}{1 + \exp\left(\alpha + \exp(\beta) * \log\left(\frac{d_j}{d_{ref}}\right)\right)},$$

with bivariate normally distributed parameters (α, β) using the following parameterization:

- preselected dose level $d_j \in \{10 \text{ mg}, 20 \text{ mg}, 35 \text{ mg}, 50 \text{ mg}\}$ subject to change by SMC)
- Reference dose $d_{ref} = 90 \text{ mg}$
- $E(\alpha) = -0.708$, $E(\beta) = -0.389$
- $SD(\alpha) = 1.2$, $SD(\beta) = 0.9$, $Cov(\alpha, \beta) = 0$.

The target DLT toxicity is 25%. The following toxicity regions for use in dose suggestion will be defined:

Toxicity Intervals	Probability of DLT	Loss term (weight in loss function)
Under-Dosing	[0.0, 0.20]	1
Targeted toxicity	(0.20, 0.35]	0
Excessive toxicity	(0.35, 0.60]	2
Unacceptable toxicity	(0.60, 1.00]	3

Recommendation on the next dose level by the model is determined as follows:

- Select the dose level that minimizes the loss function. The loss function is defined as the sum of products of the probability to lie within each of the toxicity regions, and the associated loss term:

$$1 \times P(\text{under-dosing}) + 0 \times P(\text{targeted toxicity}) + 2 \times P(\text{excessive toxicity}) + 3 \times P(\text{unacceptable toxicity}).$$

The model will be provided with the following preselected dose levels: 10 mg, 20 mg, 35 mg and 50 mg. The set of doses can be changed any time by the SMC.

The SMC will be notified of a potential candidate dose for MTD once

- the upper bound of the 95% credible interval of a potential MTD is not more than 40% and the estimated DLT probability for the suggested MTD is above or equal to 17%.

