$0 * P(\text{target dosing (estimated DLT rate in (0.2-0.35)}) + 1 * P(\text{under dosing (estimated DLT rate in [0-0.2])}) + 2 * P(\text{for over dosing (estimated DLT rate in (0.35-0.6])}) + 3 * P(\text{excessive dosing (estimated DLT rate in (0.60-1])})$.

The recommended dose level resulting from the model for the next cohort is the dose with the lowest loss function. This Bayesian escalation approach will be used to assist the SMC to select the next dose from a predicted set of acceptable doses, i.e., 10 mg, 20 mg, 35 mg, 50 mg. It is possible to choose a dose(s) not within the pre-specified dose-escalation plan. In this case the estimated posterior probabilities of the selected dose will also be provided to the SMC.

The model will continue to be updated at each SMC until the SMC has decided to stop dose escalation.

Prior distribution and likelihood are used to calculate the posterior probabilities based on Bayes theorem.

The likelihood is defined based on a binomial distribution, modelling the rate of subjects with at least 1 DLT.

The relationship between dose and toxicity rate is defined by

$$P(DLT|d_j, \alpha, \beta) = \frac{\exp\left(\alpha + \exp(\beta) * \log\left(\frac{d_j}{d_{ref}}\right)\right)}{1 + \exp\left(\alpha + \exp(\beta) * \log\left(\frac{d_j}{d_{ref}}\right)\right)}$$

Where $d_j \in \{10 \text{ mg, 20 mg, 35 mg, 50 mg}\}$ (or different) and (α, β) are bivariate normally distributed. Reference dose d_{ref} is 90 mg. The chosen prior for monotherapy escalation has the following parameters

$E(\alpha) = -0.708$,

$E(\beta) = -0.389$,

$SD(\alpha) = 1.2$, $SD(\beta) = 0.9$, $Cov(\alpha, \beta) = 0$.

The prior distribution has not been changed compared to the protocol defined.

CCI

CONFIDENTIAL
INFORMATION

18/38

M3258

First in Human Dose Escalation of M3258 as a Single Agent and Expansion
Study of M3258 in Combination with Dexamethasone

MS201814-0010

Version 2.0

Handling of changes in regimen

For different regimens, separate models will be used. In general, the same specifications outlined above will be used for each of these models, applicable to the dose given on the treatment days, unless otherwise specified. This means that in a once daily (QD) regimen, 90 mg as reference dose refers to the dosing of 90 mg daily. In a twice weekly regimen (on day 1,4,8,11, etc) the 90 mg reference dose refers to a dosing of 90 mg on day 1, day 4 etc. The approach is not considering weekly cumulative dosing.

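### The Part A model rule always names a dose: on the preselected set it returns 10 mg even after 3/3 or 6/6 DLTs at 10 mg, and it has no way to report that no dose is suggested.

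*Protocol*

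**What the plan says.** **The rule.** Protocol 9.4.2 reads: "The dose suggested by the model for the next cohort will be the dose with minimal Bayesian Risk (among all considered doses". Appendix 10 reads: "Select the dose level that minimizes the loss function". Section 15.1 of the SMC analysis plan (SAP Appendix 18.1) gives the same lowest-loss rule. None of the three adds a further condition.

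**The dose set.** Appendix 10: "The model will be provided with the following preselected dose levels: 10 mg, 20 mg, 35 mg and 50 mg", followed by "The set of doses can be changed any time by the SMC". Section 4.1 lets the SMC go lower, to "deescalation of the dose potentially down to 1mg", and section 6.1 lists 1 mg and 5 mg capsules.

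**Limits elsewhere.** Other model-based decisions in the plan carry a limit or a null result:
- RDE selection (4.1): median DLT rate at most 25% and 75th percentile below 30%.
- Dose increase at the Part B interim (9.4.1): 75th percentile below 30%.
- Part B safety stopping (7.1): "The chance is $>80\%$ that the true DLT rate is $\geq 30\%$ (based on Bayes model".
- MTD notification (Appendix 10): upper 95% bound not above 40%.
- MTD derivation (SAP 15.1): no MTD is suggested if the estimates at all tested doses are below 17%.

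**Role of the SMC.** It may choose another dose up to 50 mg (9.4.2), change the regimen, or recommend ending enrolment (9.2).

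**The concern.** The rule uses only the ordering of the losses and ignores their level. Once most of the posterior lies above a DLT rate of 35%, a higher dose only moves probability from the band weighted 2 to the band weighted 3. The lowest dose on the list therefore wins, however bad it looks. The suggestion then stops responding to further toxicity in the very situation where a first-in-human committee most needs a signal. Section 2.2 itself anticipates a steep dose-toxicity relationship. In that situation the line headed as the model's recommendation would name a dose that the same model judges very likely too toxic.

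**Working it through.** **Inputs.** All are in Appendix 10 and are repeated in the SMC analysis plan, section 15.1.
- Model: logit p(d) = α + exp(β)·log(d/d_ref); "Reference dose d_{ref} is 90 mg".
- Prior: α ~ N(−0.708, 1.2²), β ~ N(−0.389, 0.9²), independent.
- Loss = 1·P(p ≤ 0.20) + 0·P(0.20 < p ≤ 0.35) + 2·P(0.35 < p ≤ 0.60) + 3·P(p > 0.60).
- Likelihood: binomial. The posterior was computed on a 1601 × 1601 grid and cross-checked with 4 million prior draws.

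**Step 1: reproduce the plan's own figures.** Protocol 9.4.2 gives prior means of 15/19/24/28% and medians of 8/13/18/22% at 10/20/35/50 mg. The grid gives means of 14.7/18.8/23.5/27.4% and medians of 7.9/12.3/17.5/22.1%. The model is reproduced to within a percentage point.

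**Step 2: the rule on the preselected set.**
- After 3/3 at 10 mg, the probabilities of the four bands at 10 mg are 0.027, 0.110, 0.386 and 0.476. Loss = 0.027 + 2 × 0.386 + 3 × 0.476 = 2.227 (2.228 before rounding).
- After 6/6, the bands are 0.000, 0.011, 0.188 and 0.801. Loss = 2 × 0.188 + 3 × 0.801 = 2.779 (2.778 before rounding).

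| DLTs at 10 mg | Loss at 10 / 20 / 35 / 50 mg | Suggested | Mean rate at 10 mg | P(rate ≥ 30%) at 10 mg |
|---|---|---|---|---|
| 2/3 | 1.469 / 1.725 / 1.954 / 2.094 | 10 mg | 40.1% | 0.66 |
| 3/3 | 2.228 / 2.438 / 2.578 / 2.650 | 10 mg | 57.5% | 0.91 |
| 4/6 | 1.895 / 2.187 / 2.388 / 2.492 | 10 mg | 49.3% | 0.87 |
| 5/6 | 2.427 / 2.619 / 2.732 / 2.785 | 10 mg | 60.8% | 0.97 |
| 6/6 | 2.778 / 2.869 / 2.915 / 2.934 | 10 mg | 71.8% | 0.995 |

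3/6 also returns 10 mg. The largest possible loss is 3, so after 6/6 all four doses are close to the worst score and one is still named.

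**Step 3: extend the set to 1 and 5 mg.** After 3/3 the losses are 1.587 at 1 mg and 2.006 at 5 mg, so the suggestion moves to 1 mg with a posterior mean of 41.6%. After 6/6 it is again 1 mg (loss 2.227, mean 57.4%). The 10 mg answer depends on the dose list. The missing null output does not.

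**Step 4: what the Part B criterion would do as a filter (illustration only).** Drop any dose with P(rate ≥ 30%) above 0.80, then minimise the loss.

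| DLTs at 10 mg | Present set | P(rate ≥ 30%) at 1 mg | Set with 1 and 5 mg added |
|---|---|---|---|
| 3/3 | none (0.91 at 10 mg, higher above) | 0.66 | 1 mg |
| 4/6 | none (0.87) | 0.51 | 1 mg |
| 5/6 | none (0.97) | 0.74 | 1 mg |
| 6/6 | none (0.995) | 0.90 | none |

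After 2/3 (0.66) the filter does not exclude 10 mg. After 0/3 the probability is at most 0.22 at every considered dose, so the filter excludes nothing.

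**The case against.** The strongest reply is that the suggestion does not decide anything. The SMC adjudicates each DLT, and it receives DLT probabilities for candidate doses (protocol 6.6) and the 2.5, 25, 50, 75 and 97.5% posterior quantiles at each predefined dose (SMC analysis plan 15.1). After 3/3 the 10 mg line would show a median of 59%, quartiles of 44 and 72%, and a 95% interval of 19 to 90%. No committee would miss that. It may override the model, add doses or end enrolment, and the limits in 4.1 keep such a dose from becoming the RDE. This stands, and it limits the point to the quality of the output.

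The second reply is that the difference between the parts is deliberate. Section 9.4.2 says additional stopping rules apply in Part B. After the run-in, Part B enrols without pausing, so a numeric trigger is needed to force a pause. In Part A the SMC normally meets between cohorts. This is a fair reason why Part A has no pause trigger. It does not explain why a dose suggestion should be unable to come back empty.

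Third, a preselected list that the SMC may change at any time does not contradict de-escalation to 1 mg. That is correct: the default output covers less than the range open to the SMC, which is a gap and not a conflict.

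Fourth, 6/6 at 10 mg would normally require the SMC to have treated a second cohort at 10 mg after a bad first one, so 3/3 is the more realistic case. Finally, the SMC charter is not among the documents and may hold Part A stopping guidance.

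**Conclusion.** The point holds for the model output as specified. On the preselected set the rule returns 10 mg after 2/3, 3/3, 3/6, 4/6, 5/6 and 6/6 DLTs at 10 mg, and on any non-empty set it cannot report that no dose is suggested. The posterior figures rest on the prior in Appendix 10 and on every participant counted being DLT-evaluable. The absence of a null output rests only on the rule's wording.

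Three stronger readings are not supported:
- A reader might infer that the trial would treat the next cohort at 10 mg after 3/3. It would not do so automatically, because the decision belongs to the SMC.
- A reader might infer that Part A has no stopping provision anywhere. That can be said only of numeric, model-based rules in the documents available here.
- A reader might infer that the Part B criterion is the right one for Part A. The documents do not say so, and its effect depends heavily on the dose list (step 4).

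SAP section 7 records that the study stopped before Part A met its primary objective. The practical weight therefore lies in how earlier model suggestions are read and in any reuse of the design.

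**What to change.** Reconcile protocol 9.4.2, Appendix 10 and SMC analysis plan 15.1 with the plan's other model-based limits (4.1, 7.1, 9.4.1) and with the dose range in 4.1. Two changes to the output follow:
- The Part A model result can state that no dose is suggested.
- Beside the minimum-loss dose, it reports the model probability that the DLT rate is 30% or more at each considered dose.

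Which limit applies, which doses belong in the default set, and what action follows are for the sponsor and the SMC to state. They should set the limit and the dose set together. Used as a filter, the Part B criterion gives no dose after 3/3 and after 4/6 or more on the present set. With 1 and 5 mg included, among these outcomes it does so only after 6/6.

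The cost is a few sentences, a small addition to the code and no extra participants. The downsides are one more output for the SMC to review, and a suggestion that can differ from the present one when DLTs occur at 10 mg.
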